The outcome variable is the presence of CPSP assessed 3 months after surgery and defined as an average pain intensity of at least 3 on the NRS scale (11-point one-dimensional pain scale) in the last three days, and pain localized to the surgical field (or in the lesion area) projected into the innervation territory of a nerve located in this area or referred to a dermatome.

Separate prediction models will be developed using data derived from surveys conducted at the relevant time points for the development of the risk index.

The sample size of the development dataset must be large enough to develop a prediction model equation that is reliable when applied to new individuals in the target population. The Authors estimate to include approximately 1500 patients to develop a clinical prediction model of CPSP three months after surgery.

The Authors estimate that at least 10 Centers are needed to enroll the intended study population.

The total expected time, from the date of project approval to the production of the draft manuscript, is 24 months.

Background

Chronic post-surgical pain (CPSP) is a common and disabling postoperative complication; it is defined as pain that develops or increases in intensity after surgery and persists at least 3 months after surgery. It can

be localized in the surgical field, projected into the innervation territory of a nerve located in this area, or referred to a dermatome [1].

CPSP affects millions of individuals worldwide, with an estimated incidence between 10 and 50%, depending on the surgery performed [2]. It is rated serious by 2-10% of patients [2;3]. Furthermore, CPSP is considered a serious medical but also social and economic problem [4;5] and represents a significant portion of medical prescriptions and healthcare costs [6]. Furthermore, in combination with psychological consequences, chronic pain significantly impairs the quality of life [7] and productivity, exposing patients to the risk of drug addiction [8].

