- Surgical complications (Y/N)
- Infectious complications related to surgery (Y/N)
- Malignancy (Y/N)

Questionnaires:

• Douleur Neuropathique in 4 questions (DN-4)

Outcome variable

The outcome variable is the presence of CPSP assessed 3 months after surgery and defined as an average pain intensity of at least 3 points on the NRS scale (one-dimensional pain scale - from 0 to 10 points) in the last three days and pain localized to the surgical field (or in the lesion area) projected into the innervation territory of a nerve located in this area, or referred to a dermatome [30;31].

Development of the risk index

Separate prediction models will be developed using data derived from investigations conducted at the relevant time points.

(1) Primary version of the risk index, made up of items derived from a systematic bibliographic search (compilation of the item pool).

(2) In a second phase, the Authors will analyze the associations between each of these indices and the probability of CPSP 3 months after surgery (dichotomous variable), evaluated using logistic regression models.

(3) Items that were found to be significant in the bivariate analyses will then be analyzed multivariately (logistic regression models).

(4) In a fourth step, the Authors will safeguard the results of the multivariate analyses by calculating the area under the ROC curve of the model, and then, the cut-off score for a high risk of developing CPSP will be identified with an optimal compromise between sensitivity and specificity.

(5) Finally, the items that will generate significant predictive factors in the logistic regression analyses will be collected into an index. For each value of this index, the Authors will calculate the proportion of patients who reported CPSP at 3 months after surgery.

Statistical analysis of results

The study population will be described by summarizing the variables collected in each period of evaluation of the subject (preoperative, perioperative before surgery, perioperative after surgery, three months post-operatively after surgery). In particular, the discrete variables will be reported in terms of absolute and relative frequency, and the continuous variables will be summarized via mean and standard deviation or via median and interquartile range, based on the symmetry of each distribution.

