The study population will be stratified based on the presence/absence of CPSP three months after surgery, and a comparison will be made between the two groups. In detail, the Student's T test for independent samples will be used in the case of normally distributed variables (normality assessed using the Kolmogorov-Smirnov test), the non-parametric Wilcoxon-Mann-Whitney test in the case of non-normally distributed variables, the Pearson Chi-Square in case of discrete variables or Fisher's exact test if the expected frequency is low.

Univariate and multivariate logistic regression models will be used to study the association between the probability of CPSP three months after surgery (dependent variable) and the collected variables (independent variables). The results of each model will be reported in terms of model parameters and odds ratios and their 95% confidence intervals. For each logistic model, the discriminated ability will be evaluated via the C-statistic of the area under the ROC curve and calibration via the Hosmer-Lemeshow test. To identify significant (preoperative and intraoperative) predictors of CPRS three months after surgery, backward elimination will be used with the threshold of 0.05 as the level to remain in the model. The parameters of the multivariate logistic regression model resulting from this process will be used to assign a score to each predictor. Internal validation will be conducted using bootstrapping to correct for optimism.

Given the observational nature of the study, as well as the large sample size and multicenter nature, any variable reporting a high proportion of missing values (>25%) will be eliminated from the analyses. Subjects in which more than half of the variables are missing will be excluded from the analysis. Lower proportions will lead to the use of the statistical technique of multiple imputations of missing data, assuming that the missing data are random (independent of the missing value, but dependent on other variables). Based on the total proportion of missing data, if this is relatively low (less than 5%) the possibility of analyzing only those subjects with all available data may also be taken into consideration.

For all statistical analyses, the significance level is set at p < 0.05 and the tests used are two-tailed.

Power analysis

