The sample size of the development dataset must be large enough to develop a prediction model equation that is reliable when applied to new individuals in the target population.

The authors estimate that approximately 1500 patients are necessary to develop a logistic model for clinical prediction of CPSP (presence/absence) three months after surgery.

The estimate of the sample size was performed following the methodological recommendations of Riley [33] and hypothesizing two scenarios with a cumulative incidence of CPSP 3 months after the intervention of 10% and 50%. It was necessary to hypothesize two scenarios since the aggregate incidence of CPSP in the

target population is not known in the literature. The information is available only based on the type of surgery and the estimate varies between 10% and 50%.

Assuming an incidence of 50% and that the final predictive model can explain more than 15% of the variability with 15 candidate parameters (risk of overfitting), a sample size of 1124 subjects is estimated for the development of a logistic predictive model, corresponding to 37 subjects with CPSP per parameter.

Assuming an incidence of 10% and that the final predictive model can explain more than 15% of the variability with 15 parameters, a sample size of 1799 subjects is estimated for the development of a logistic predictive model, corresponding to 12 subjects with CPSP by parameter. The sample size is reduced to 1440 individuals for the development of a final predictive model with 12 parameters.

Given the uncertainty on the estimated incidence of CPSP three months after surgery, a sample size of, at least, 1500 individuals is therefore sufficient to meet the main objective of the study.

Expected number of centers to enroll

Authors estimate that, at least, 10 centers are needed to enroll the study population.

Schedule

The calendar will be organized into three-time windows:

• First phase - Authorization from the Local Ethics Committee of the participating Center, patient enrollment, and first evaluations: from the 1st to the 12th month from the date of project approval.

• Second phase - completion of follow-up and sending of complete clinical documentation from the registered Centers: from the 12th month to the 18th month from the date of project approval.

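### By the plan's own calculation, 1500 patients support 12 or fewer candidate parameters at 10% incidence; nothing holds the candidates to 12, so the claim of sufficiency does not follow

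*Combined protocol and SAP*

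**What the plan says.** The Power analysis section takes two incidence scenarios, 10% and 50%, because the overall incidence in the target population is unknown, and cites the Riley recommendations. Its figures are:

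- 50% incidence: "with 15 candidate parameters (risk of overfitting), a sample size of 1124 subjects is estimated".
- 10% incidence: "with 15 parameters, a sample size of 1799 subjects is estimated for the development of a logistic predictive model".
- 10% incidence, smaller model: "The sample size is reduced to 1440 individuals for the development of a final predictive model with 12 parameters".

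It concludes that "a sample size of, at least, 1500 individuals is therefore sufficient to meet the main objective of the study".

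On model structure, the Abstract says "Separate prediction models will be developed using data derived from surveys conducted at the relevant time points for the development of the risk index", and the section Development of the risk index says much the same: "Separate prediction models will be developed using data derived from investigations conducted at the relevant time points". That section then lets items into the multivariable model if they are significant one at a time. Statistical analysis of results adds: "To identify significant (preoperative and intraoperative) predictors of CPRS three months after surgery, backward elimination will be used", with 0.05 as the level for staying in, and builds the score from the resulting model. Neither section caps the number of candidates. Data collection lists the items recorded at each time without marking which are candidate predictors.

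**The concern.** The step from 1799 to a planned 1500 rests entirely on going from 15 parameters to 12. That step is valid only if the plan is bound to 12 or fewer candidates, and it is not. The text attaches the 12 to the final model, whereas the calculation is about candidates, as the section itself says in the 50% scenario. Univariable screening and backward elimination both look at the outcome. A model that reaches 12 terms by those routes carries the overfitting of the full list it started from.

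The sentence on sufficiency is the plan's only justification of its sample size for the prediction model. If the candidates exceed what 1500 can support, the score will be more overfitted than the Power analysis section implies. The estimate of occurrence, the other part of the main objective, is not affected: a margin of ±5 percentage points needs at most (1.96/0.05)² × 0.25 = 384.2, so 385 patients.

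**Working it through.** **Inputs.** From the Power analysis section: incidence p of 10% or 50%, 15% of variability explained, P = 15 or 12 parameters, N = 1500. Inferred, because they reproduce the printed figures: target shrinkage S = 0.9, and 15% read as a share of the maximum Cox-Snell R².

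**Formulas.**

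- max R² = 1 − exp{2[p ln p + (1 − p) ln(1 − p)]}
- R²cs = 0.15 × max R²
- n = P / [(S − 1) ln(1 − R²cs/S)]

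**Reproducing the plan.**

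- p = 0.5: max R² = 0.75, R²cs = 0.1125. P = 15 gives 1123.3 (printed 1124).
- p = 0.1: max R² = 0.478, R²cs = 0.0717, rounded to 0.072. P = 15 gives 1799.0 (printed 1799) and P = 12 gives 1439.2 (printed 1440). Unrounded, these are 1806.6 and 1445.3.

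The other criteria of the same method give smaller numbers (at most 856 at 50% and 598 at 10% for P = 15), so the shrinkage criterion governs.

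**What 1500 supports.** Solving for P, with every patient's outcome observed: 12.5 at 10%, 16.7 at 20% and 20.0 at 50%, so at most 12, 16 and 20 candidates. At 10%, P = 13 already needs about 1560. For P = 15 at 10%, 1500 is 1799 − 1500 = 299 short (299/1799 = 17%).

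**Loss to follow-up.** The section makes no allowance for it. The margin over 1440 is 60 patients, or 60/1500 = 4%. With 10% to 20% loss at three months (an assumption), the limit falls to about 11 to 10 candidates at 10% incidence and 18 to 16 at 50%.

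**Candidates in the item lists.** Counting k categories as k − 1 terms and each yes/no item as one:

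- Preoperative: age 2, BMI 2, 11 single items = 15.
- Before surgery: site 5, technique 2, anaesthesia 3, 5 single items = 15.
- After surgery: coverage of analgesia 2, 5 single items = 7.

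With age and BMI as single ordered terms (an assumption) the preoperative count is 13, still above 12.

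**If models are separate and each uses only its own items.**

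| Parameters | 10% | 20% | 50% |
|---|---|---|---|
| 7 | about 840 | – | about 525 |
| 15 | 1799 | 1347 | 1124 |

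The 7-parameter model is covered throughout. For 15 parameters, 1500 is reached at p = 0.150. At N = 1500 the expected shrinkage is 0.88 at 10% and 0.92 at 50%. At 10%, the gap closes if the model explains about 18% of maximum R² (n about 1493).

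**If preoperative and before-surgery items are pooled.** 15 + 15 = 30 candidates need 3598 at 10%, 2693 at 20% and 2247 at 50%. Expected shrinkage at N = 1500 runs from 0.79 (10%) to 0.86 (50%). A narrower pool of 27, without ERAS, premedication and postoperative prescription, still needs 3238 at 10% and 2022 at 50%. At 50% incidence, 30 candidates would need about 1481 if R² were 22% of its maximum; at 10% it would take about 34%.

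**The case against.** The best defence is that the shortfall is small on the better-supported reading. Two sections announce separate models, the preoperative list gives the 15 parameters used in the calculation, and 1500 is enough for 15 from about 15% incidence. The 10% scenario is the bottom of a range quoted by type of surgery. A study of any elective surgery would sit there only if nearly all patients had the lowest-incidence procedures. The 15% is also worded as a floor, so a better-fitting model would need fewer patients, and bootstrap correction for optimism is planned.

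Most of this stands and limits the severity, but it does not rescue the conclusion. The plan chose 10% as a design scenario because it did not know the incidence, and it argues sufficiency in that scenario only by moving to 12. The bootstrap measures and corrects optimism; it does not change how many candidates 1500 supports. Nor does the wording that 1500 is a minimum help, since Data collection ends inclusion once the protocol's total is reached. Dropping variables with more than 25% missing could shorten the list, but by an unknown amount.

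A reader might infer that 1500 fails at every incidence from 10% to 50%. The documents do not support that without conditions. It needs a pooled selection of about 30 candidates, which means counting the before-surgery items as intraoperative. The text allows that reading but does not settle it: the words in parentheses may only name types of predictor. It also needs R² held at 15% of its maximum. Nor do the printed sample sizes contain an arithmetic error, or the 12 events per parameter, which is right for the 1799 patients it belongs to.

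**Conclusion.** The statement of sufficiency is wrong as written and should be corrected. Under the plan's own inputs, 1500 covers the 10% scenario only with 12 or fewer candidate parameters, and no section imposes that limit.

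The size depends on a choice the plan leaves open. With separate models the deficit is modest and lies only below about 15% incidence. With a pooled selection it covers the plan's whole incidence range at the 15% input, though a higher R² could close it at the 50% end.

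The result rests on the two inferred inputs, which reproduce all three printed figures, and on the counting of category terms shown above. The loss rates are illustrative and do not carry the conclusion.

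**What to change.** No extra patients are needed.

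1. Replace the sentence on sufficiency with the number of candidates the sample supports. For example: *With a shrinkage target of 0.9 and R² at 15% of its maximum, 1500 patients with an observed three-month outcome support at most 12 candidate parameters at 10% incidence, 16 at 20% and 20 at 50%; fewer after loss to follow-up.* The authors should confirm the two inferred inputs.
2. Reconcile the Abstract and Development of the risk index with Statistical analysis of results: say whether the score comes from separate models or one pooled model, and whether later models carry earlier items forward.
3. Before outcomes are analysed, fix a literature-based candidate list for each model within that limit, counting every category term. Collapsing the categories of site, technique or anaesthesia is one way to do it.

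The cost is some rewriting, a less favourable stated figure, and some items collapsed or dropped. Keeping all items with a penalised fit is an option only. It would change the planned backward elimination and scoring, and it would not make 1500 meet the 0.9 target for 30 candidates, so the expected shrinkage would have to be reported alongside.
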